6.5 Medication error and overdose

6.5.1 Medication error

For the purposes of this clinical study, a medication error is an unintended failure or mistake in the treatment process for the study drug(s) that either causes harm to the patient or has the potential to cause harm to the patient.

A medication error is not lack of efficacy of the drug, but rather a human or process related failure while the drug is in control of the study site staff or patient.

Medication error includes situations where an error has:

- occurred
- was identified and intercepted before the patient received the drug
- did not occur, but circumstances were identified that could have led to an error

Examples of events to be reported in clinical studies as medication errors:

- Drug name confusion
- Dispensing error e.g., medication prepared incorrectly, even if it was not actually given to the patient
- Drug not administered as indicated, for example, wrong route or wrong site of administration
- Drug not taken as indicated e.g., tablet dissolved in water when it should be taken as a solid tablet
- Drug not stored as instructed e.g., kept in the fridge when it should be at room temperature
- Wrong patient received the medication
- Wrong drug administered to patient

Examples of events that do not require reporting as medication errors in clinical studies:

- Patient accidentally missed drug dose(s) e.g., forgot to take medication
- Accidental overdose (will be captured as an overdose see Section [6.5.2](#))

- Patient failed to return unused medication or empty packaging
- Errors related to background and rescue medication, or standard of care medication in open label studies, even if an AZ product

Medication errors are not regarded as AEs but AEs may occur as a consequence of the medication error.

If a medication error occurs in the course of the study, then the Investigator or other site personnel informs the Sarah Cannon representatives within 1 day, i.e., immediately but no later than 24 hours of when he or she becomes aware of it. The Sarah Cannon representative works with the Investigator to ensure that all relevant information is completed within 1 to 5 calendar days if there is an SAE associated with the medication error (see Section 6.2) and within 30 days for all other medication errors.

6.5.2 Overdose

A dose of AZD1775 in excess of that specified according to the protocol will constitute an overdose. There is currently no known antidote to AZD1775, and the treatment of overdose should be supportive for the underlying symptoms. To date, there has been one patient who has experienced an overdose with AZD1775 which was associated with adverse events.

Overdoses with non-AZ products used in combination or comparative studies should be managed according to the product label.

Such overdoses should be recorded as follows:

- An overdose with associated AEs is recorded as the AE diagnosis/symptoms on the relevant AE modules in the eCRF and on the Overdose eCRF module.
- An overdose without associated symptoms is only reported on the Overdose CRF module.

If an overdose of AZD1775 occurs in the course of the study, then the Investigator or other site personnel will inform the Sarah Cannon Safety Department immediately or **no later than 24 hours** of when he or she becomes aware of it. All overdoses of AZD1775 have to be reported by completing an Overdose Form. The Sarah Cannon Safety Department representative works with the Investigator to ensure that all relevant information is provided.

For overdoses associated with SAE, standard reporting timelines apply (see Section 6). For other overdoses, reporting should be done within 24 hours.

Additional PK samples should be collected for any AE possibly related to AZD1775; please refer to Section 5.4 for further guidance.

6.6 Pregnancy

All pregnancies and outcomes of pregnancy should be reported to the Sarah Cannon Safety Department.

6.6.1 Maternal exposure

If a patient becomes pregnant during the course of the study, study treatment should be discontinued immediately.

Pregnancy itself is not regarded as an AE unless there is a suspicion that the IP under study may have interfered with the effectiveness of a contraceptive medication. Congenital abnormalities/birth defects and spontaneous miscarriages should be reported and handled as SAEs. Elective abortions without complications should not be handled as AEs. The outcome of all pregnancies (spontaneous miscarriage, elective termination, ectopic pregnancy, normal birth or congenital abnormality) should be followed up and documented even if the patient was discontinued from the study.

If any pregnancy occurs in the course of the study, then Investigators or other site personnel inform the Sarah Cannon Safety Department immediately, or **no later than 24 hours** of when he or she becomes aware of it.

The Sarah Cannon Safety Department representative works with the Investigator to ensure that all relevant information is provided.

The same timelines apply when outcome information is available.

6.6.2 Paternal exposure

Male patients should refrain from fathering a child or donating sperm during the study and for three months following the last dose of study treatment.

Pregnancy of the patient's partner is not considered to be an AE. However, the outcome of all pregnancies (spontaneous miscarriage, elective termination, ectopic pregnancy, normal birth or congenital abnormality) should if possible be followed up and documented. To capture information about a pregnancy from the partner of a male patient, the male patient's partner's consent must be obtained to collect information related to the pregnancy and outcome; the male patient should not be asked to provide this information. The outcome of any conception occurring should be followed up and documented.

6.7 Management of IP related toxicities

Toxicity will be assessed utilising the NCI CTCAE v4.03 (<http://evs.nci.nih.gov/ftp1/CTCAE/CTCAE>), unless otherwise specified.

Dose adjustments will be based on the organ system exhibiting the greatest degree of toxicity. Dose reductions or holds and initiation of supportive care are allowed as clinically indicated by the treating physician. Additional unscheduled PK samples should be collected for any AE

possibly related to AZD1775. The date and time of last study drug administration should be collected and recorded on an ‘Unscheduled PK’ sample eCRF page. The additional PK samples should not be taken if the last dose of study drug(s) was administered > 1 week prior to the event.

A maximum of 2 dose reductions for AZD1775 will be allowed. Patients requiring >2 dose reductions will be discontinued from the study drug.

There are different doses and schedules being evaluated currently. Dose should be reduced to a previous dose level for a toxicity. Patients starting at 125 mg BID can be dose reduced to 125 mg QD if needed for management of toxicity. Patients on 150 mg BID can be dose reduced to 125 mg BID and potentially 150 mg QD if needed for management of toxicity. Patients on 200 mg QD can be dose reduced to 150 mg QD and potentially 125 mg QD if needed for management of toxicity.

Any patient requiring a toxicity-related dose delay of more than 21 days from the intended day of the next scheduled dose must be discontinued from the study unless there is approval from the Medical Monitor for the patient to continue.

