4.3.2.3 Final Protocol Visit and Beyond

The Final Protocol Visit (FPV) requirement applies only to patients who continue AZD1775 after the implementation of the Clinical Study Protocol (CSP) Version 5. Patients should return to the clinic soon after the CSP Version 5 is implemented in order to be re-consented on the associated updated ICF.

Beyond the FPV, patients may continue to receive AZD1775 if they are deriving clinical benefit, in the opinion of the Investigator, and not fulfilling any of the discontinuation criteria. Such patients are to be treated in accordance with local practice and as deemed appropriate by the Investigator to ensure continued safety monitoring of the patient while receiving the investigational product. It is recommended to continue observing ongoing patients at the frequency indicated within the study plans as described in [Table 3](#) and [Table 4](#). Restrictions regarding concomitant medications (refer to Section [7.8.2](#)) will be followed while the patient is receiving AZD1775. A change in AZD1775 dose/schedule should only occur for safety reasons, based on the Investigator's judgement, and should generally follow the approach for dose reduction and discontinuation as described in this protocol. Combining AZD1775 with other anti-cancer therapy is not allowed.

If a patient is no longer receiving benefit from AZD1775 beyond the FPV in the opinion of the treating physician, then the study drug should be stopped. The Investigator will inform AstraZeneca when a patient discontinues the study drug. Patients must return unused medication during routine clinic visits, and drug accountability information must continue to be collected in patient source documents until the patient discontinues treatment. In addition, provided that a patient gives proper informed consent, a plasma isolation (ctDNA) blood sample for future biomedical research should be obtained at the time of AZD1775 discontinuation, if due to disease progression. Patients will continue to be monitored for all SAEs, pregnancies, and overdoses for 30 days after the last dose of the investigational product.

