6.7.1 Dose modifications and guidance

Substantial acute toxicities should be managed as medically indicated and with temporary suspension of study, as appropriate. Dose reductions and holds are allowed as clinically indicated by the treating physician and if in line with [Table 9](#) and [Table 10](#). For each patient, a maximum of 2 dose reductions will be allowed as presented in [Table 7](#) and [Table 8](#).

Table 7 AZD1775 BID (Cohorts BID 1 and 2) Dose Level Reductions^a

	AZD1775 STARTING DOSE	AZD1775 -1 DOSE LEVEL
AZD1775 BID regimens	125 mg BID	TBD ^b
	150 mg BID	TBD ^b

a Full details of the AZD1775 BID regimens are provided in [Figure 1](#) and [Figure 2](#).

b If dose reduction required below 150 or 125 mg, this is to be discussed on a case by case basis with Medical monitor

Table 8 AZD1775 QD (Cohorts QD 1.1, 1.2, 2.1, 2.2, 2.3, 3.1, 3.2, 3.3, 4.1, 4.2) Dose Level Reductions^a

	AZD1775 STARTING DOSE	AZD1775 -1 DOSE LEVEL	AZD1775 -2 DOSE LEVEL
AZD1775 QD regimens	200 mg QD	TBD ^b	TBD ^b
	250 mg QD	TBD ^b	TBD ^b
	300 mg QD	250 mg QD ^b	TBD ^b

Table 8 AZD1775 QD (Cohorts QD 1.1, 1.2, 2.1, 2.2, 2.3, 3.1, 3.2, 3.3, 4.1, 4.2) Dose Level Reductions^a

AZD1775 STARTING DOSE	AZD1775 -1 DOSE LEVEL	AZD1775 -2 DOSE LEVEL
400 mg QD	300 mg QD	250 mg QD ^b

a Full details of the AZD1775 QD regimens are provided in [Figure 3](#) and [Figure 4](#).

b If dose reduction required below 250 mg, this is to be discussed on a case by case basis with Medical Monitor

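### Section 6.7 names dose-reduction steps for 125 mg BID, 150 mg BID and 200 mg QD with no Medical Monitor condition, while Tables 7 and 8 list the same reductions as TBD and require Medical Monitor discussion.

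*Protocol*

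**What the plan says.** Section 6.7 sets the ceiling, "A maximum of 2 dose reductions for AZD1775 will be allowed", and a general rule, "Dose should be reduced to a previous dose level for a toxicity". It then names steps for three starting doses:

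- Cohort BID 1 gets a single step: "Patients starting at 125 mg BID can be dose reduced to 125 mg QD if needed for management of toxicity".
- Cohort BID 2 gets two, with the second hedged: "Patients on 150 mg BID can be dose reduced to 125 mg BID and potentially 150 mg QD if needed for management of toxicity".
- Cohorts QD 1.1 and QD 1.2 also get two, again with the second hedged: "Patients on 200 mg QD can be dose reduced to 150 mg QD and potentially 125 mg QD if needed for management of toxicity".

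No consultation is attached to any of these. The section calls for Medical Monitor approval only when a toxicity-related delay exceeds 21 days and the patient is to continue.

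Section 6.7.1 repeats the limit of two reductions and says they are presented in Tables 7 and 8. Table 7 (BID) has a single reduction column, and both rows read TBD. Its footnote begins "If dose reduction required below 150 or 125 mg" and refers the matter to the Medical Monitor case by case. Table 8 (QD) has two reduction columns. Both are TBD for 200 mg and for 250 mg, with the footnote "If dose reduction required below 250 mg, this is to be discussed on a case by case basis with Medical Monitor".

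Table 10 (neutropenia, infection, thrombocytopenia) and Table 11 (QTc prolongation) use the next lower dose level as the dose for resuming treatment after certain events. Section 4.3.2.3 says that dose changes after the Final Protocol Visit "should generally follow the approach for dose reduction and discontinuation as described in this protocol".

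**The concern.** A dose-reduction rule should tell a site what happens next and who has to agree. Here one section reads as leave to take a named step on the treating physician's judgement. The next subsection leaves the step open and requires a discussion first. Nothing in the protocol says which governs. Tables 10 and 11 rely on the next lower level without defining it, so they inherit the ambiguity at the point where a reduction is called for. What is at stake is consistent handling of the same toxicity across sites, which is a patient-safety matter in a dose-finding study.

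**Working it through.** No sample size, error rate or other statistical figure is involved, so the check is a comparison of Section 6.7 with Tables 7 and 8, by starting dose.

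| Starting dose | Cohorts (Table 1) | Section 6.7 | Tables 7 and 8 | Conflict |
|---|---|---|---|---|
| 125 mg BID | BID 1 | one named step, no consultation | one level, TBD, Medical Monitor | direct |
| 150 mg BID | BID 2 | two named steps, no consultation | one level, TBD, Medical Monitor | direct, and in number of levels |
| 200 mg QD | QD 1.1, 1.2 | two named steps, no consultation | two levels, both TBD, Medical Monitor | direct |
| 250 mg QD | QD 2.1, 2.2, 2.3 | general rule only | two levels, both TBD, Medical Monitor | with the general rule only |
| 300 mg QD | QD 3.1, 3.2, 3.3 | general rule only | first level named, second TBD | second reduction, with the general rule only |
| 400 mg QD | QD 4.1, 4.2 | general rule only | both levels named | none |

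**Size.** All three starting doses with named steps in Section 6.7 differ from the tables. In cohorts that is 1 + 1 + 2 = 4 of the 12 in Table 1. The 250 mg QD rows add 3 cohorts of the weaker kind. Section 6.7 names no step for them, but its general rule points to a previous dose level, and 200 mg QD is a listed level in Tables 1 and 12. Table 8 nevertheless says TBD.

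**Number of levels.** Two reductions is a maximum, so a single column in Table 7 does not by itself break the rule. For 125 mg BID, Section 6.7 names only one step, which matches one column. The clash is confined to 150 mg BID: Section 6.7 gives two steps, Section 6.7.1 says the tables present the reductions, and Table 7 cannot show the second.

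**Can another table settle it?** No. 150 mg QD and 125 mg QD, which Section 6.7 names as steps, are not dose levels in Table 1 or Table 12. The term used in Tables 10 and 11 therefore cannot be resolved for these patients from the cohort lists.

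**Who is still affected?** Section 4.3.2.3 refers continuing patients to Tables 3 and 4, the QD study plans, and only those two have a Final Protocol Visit column. Table 2, for BID, has none, and Table 12 marks both BID cohorts as completed. Looking forward, the point therefore concerns the QD rows: QD 1.1 and 1.2 directly, and QD 2.1 to 2.3 through the general rule.

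**The case against.** The best defence is that the two texts can be read together. Section 6.7 speaks of what can or potentially may be done, so it lists options. Tables 7 and 8 name no competing dose; they say that the choice is discussed with the Medical Monitor. On that reading, Tables 10 and 11 resolve to a Medical Monitor decision wherever a row is TBD, and Section 6.7.1 points sites to the tables.

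Much of this stands, and it limits the point. Four stronger conclusions that a reader might infer are not supported:

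- *The protocol gives different next doses for the same patient.* It does not. One text names a step and the other leaves it open. The demonstrable difference is in the approval path.
- *Seven cohorts are in direct conflict.* Only four are. The three 250 mg cohorts meet only a general sentence.
- *BID patients remain exposed after the Final Protocol Visit.* The provisions for that period point only to the QD study plans, and Section 4.3.2.3 itself asks for general adherence and leaves room for the investigator's judgement.
- *Dose-intensity and reduction summaries become inconsistent.* Section 8.4.2 summarises exposure received and whether a patient had at least one reduction. Both stay well defined whichever step was taken.

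What the defence does not remove is that the combined reading has to be supplied by the reader. A site that relies on Section 6.7 alone finds a named step and no requirement to consult, and no sentence tells it that the table footnotes override that.

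**Conclusion.** The inconsistency is real in the current text. Section 6.7 and Tables 7 and 8 set different conditions for the same reductions at 125 mg BID, 150 mg BID and 200 mg QD, which is 4 of 12 cohorts. The three 250 mg QD cohorts carry a lesser tension with the general rule, and 150 mg BID has one level too few in Table 7 for the steps that Section 6.7 names. The consequence is that sites can properly follow different approval paths for the same toxicity, including where Tables 10 and 11 prescribe a reduction. No effect on the dose-escalation rule, an endpoint or the planned exposure summaries is shown.

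Two limits apply. The steps in Section 6.7 are permissive, so this is a conflict over conditions and completeness, not between two fixed doses. A column lost from Table 7 in conversion cannot be fully excluded; its header and rows agree with each other, and the TBD conflict does not depend on it. The count is of cohorts; the protocol does not say how many patients were still on treatment at Version 5.

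**What to change.** Reconcile Section 6.7 with Tables 7 and 8 so that each starting dose has one stated path for each permitted reduction, and say in each case whether Medical Monitor discussion is required beforehand. Settle whether 150 mg BID has a second level, and make Table 7 and Section 6.7 agree on it. State how the general rule in Section 6.7 relates to the TBD entries in Table 8. Have Tables 10 and 11 refer to the reconciled path. Which steps are used, and who approves them, is for the clinical team; this review takes no view. The cost is wording in one section and two tables, plus a cross-reference in Tables 10 and 11. If an amendment is made, the QD entries matter most for patients who continue after the Final Protocol Visit.

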3.9.1 Procedures for discontinuation of a patient from investigational product

At any time, subjects are free to discontinue investigational product or withdraw from the study (i.e., investigational product and assessments – see Section 3.9), without prejudice to further treatment. A subject that decides to discontinue investigational product will always be asked about the reason(s) and the presence of any adverse events. If possible, they will be seen and assessed by an Investigator(s). Adverse events will be followed up (See Section 3.9); and all study drug should be returned by the subject.

If a subject is withdrawn from study, see Section 3.10.

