- n For the fed condition, which requires the consumption of a high-fat meal (see Section 7.3), patients will be required to fast for ≥ 10 hours prior to receiving AZD1775 until 4 hours post-dose, with the exception of a high-fat meal that should be eaten in the 30 minutes prior to AZD1775 being administered on Cycle 2 Day 1. The AZD1775 capsule should be administered 30 minutes after the start of meal consumption. If the meal is not completed within 30 minutes, AZD1775 may still be administered so long as 75% of the meal has been consumed within 45 minutes of the start of the meal (see Section 7.3).
- o Initial (i.e. baseline) tumour imaging studies (e.g. computed tomography (CT) scan of the chest and abdomen/pelvis) will be performed within 28 days prior to the first dose of study drug (AZD1775) and will be repeated at the completion of Cycle 4 (Week 8) within 7 days before starting Cycle 5. Patients with measurable or non-measurable disease will be evaluated according the RECIST v1.1. Patients with progressive disease or unacceptable toxicity should be discontinued from the study; patients with stable disease or response to therapy will continue treatment. The same method of assessment and the same technique must be used to characterize each identified and reported lesion at screening/baseline and during subsequent imaging procedures. Tumour imaging studies will be repeated every 4 cycles (8 weeks) to assess response.
- p Blood samples will be taken for plasma isolation before dosing on Cycle 1 Day 1, Cycle 2 Day 1, Cycle 3 Day 1, and on Day 1 of every 2 cycles afterwards (e.g. Cycles 5, 7 [see Section 5.5]).
- q Patients without evidence of undue toxicity may continue treatment with study drug until disease progression as long as the investigator deems that the patient is deriving clinical benefit and desires to continue therapy.
- r Patients discontinuing AZD1775 should be scheduled for an end of treatment (EOT) study visit as soon as possible after their last dose (< 30 days after finishing study treatment). If treatment is discontinued during a study visit, the EOT visit does not need to be repeated. The reason for stopping treatment and date must be recorded in the electronic case report form (eCRF).

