5.1 Efficacy assessments

5.1.1 Tumour assessments

RECIST v1.1 criteria will be used to assess patient response to treatment. The RECIST v1.1 guidelines for measurable, non-measurable, target lesions (TL) and non-target lesions (NTL) and the objective tumour response criteria (Complete Response [CR], Partial Response [PR], Stable Disease [SD] or progressive disease [PD]) are presented in [Appendix E](#).

The same method of assessment of tumour burden used at baseline (CT scans or magnetic resonance imaging [MRI] of the chest and abdomen/pelvis) must be used at each subsequent follow-up assessment (see [Table 2](#), [Table 3](#), and [Table 4](#)). Tumour imaging studies will be repeated every 8 weeks (± 1 week) relative to date of first dose for patients on the QD 5/9 treatment schema and every 9 weeks (± 1 week) relative to date of first dose for patients on the QD 5/2 treatment schema to assess response until objective disease progression as defined by RECIST v1.1 or withdrawal from study.

Categorisation of objective tumour response assessment will be based on the RECIST v1.1 criteria of response: CR, PR, SD and PD. Target lesion progression will be calculated in comparison to when the tumour burden was at a minimum (i.e. smallest sum of longest diameters previously recorded on study). In the absence of progression, tumour response (CR, PR, or SD) will be calculated in comparison to the baseline tumour measurements obtained before starting treatment.

If the Investigator is in doubt as to whether progression has occurred, particularly with regard to NTLs or the appearance of a new lesion, it is advisable to continue treatment until the next scheduled assessment or sooner if clinically indicated, and reassess the patient's status. If repeat scans confirm progression, then the date of the initial scan should be declared as the date of progression.

To achieve 'unequivocal progression' on the basis of non-target disease, there must be an overall level of substantial worsening in non-target disease such that, even in presence of SD or PR in target disease, the overall tumour burden has increased sufficiently to merit discontinuation of therapy. A modest 'increase' in the size of one or more NTL is usually not sufficient to qualify for unequivocal progression status.

It is important to follow the assessment schedule as closely as possible.

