6.7.2 Dose modifications due to haematologic toxicity

Complete blood counts (CBC) will be obtained for all patients at the beginning of each treatment cycle (Day 1). If haematologic toxicity occurs (see [Table 9](#)), treatment should be held and ANC and platelets should be monitored weekly until recovery.

Table 9 Cycle Day 1 Haematologic Dose Modifications

Treatment Day Blood Counts and Toxicity			
ANC		Platelets	Action
≥1000/μL	And	≥75,000/μL	No dose modification or interruption
<1000/μL	Or	<75,000/μL	Delay by 1 week intervals until recovery

If haematologic toxicity parameters do not recover within 21 days, the patient should be removed from the study treatment.

Table 10 Neutropenia, Infection, Febrile Neutropenia Dose Modifications and Management

Any Day	

Grade 3 neutropenic fever (ANC <1000/μL + Temperature \geq101°F [38.5°C]) or neutropenic infection
 
Documented infection with Grade 3 neutropenia (ANC <1000/μL)
 
Grade 4 neutropenia (ANC <500/μL >7 days)
 
Grade 4 thrombocytopenia (platelet count <25,000/μL >7 days)
	
Hold dose until recovery.
 
Then, upon resuming dosing, reduce AZD1775 to the next lower dose level^a.

Grade 4 febrile neutropenia or Grade 4 infection with neutropenia (both defined as septic shock)
 
Thrombocytopenic haemorrhage (gross occult bleeding) associated with a platelet count <50,000/μL
	
Discontinue treatment and follow for disease progression.

a No more than two dose reductions will be allowed for any patient. Patients requiring additional dose modifications due to toxicity will discontinue study treatment.

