6.7.3 Non-haematologic toxicity dose modifications

Substantial acute toxicities should be managed as medically indicated and with temporary suspension of investigational product, as appropriate. Dose reductions or holds and initiation of supportive care are allowed as clinically indicated by the treating physician.

Dose reductions of AZD1775 should be considered if the toxicity is considered to be related to AZD1775. Dose re-escalation is not permitted.

In general, if a patient experiences a G1/G2 non-haematological toxicity, no dose modification is required (except QTc prolongation, see table below). If a patient experiences a G3 or G4 toxicity which is not attributable to the disease or disease-related processes under investigation, dosing will be interrupted and/or the dose reduced, and supportive therapy administered as required. Any patient who develops a Grade 3 or 4 non-haematologic toxicity that does not resolve to \leq Grade 1 within 21 days should be removed from the study treatment unless approved by the Medical Monitor.

Table 11 AZD1775 dose modifications for QTc interval prolongation

Electrocardiogram QT corrected interval prolonged	
QTc Value	AZD1775

Table 11 AZD1775 dose modifications for QTc interval prolongation

Electrocardiogram QT corrected interval prolonged	
QTc 450-480 ms (males) or 470-480 ms (females)	Hold. Once QTc interval has returned to pretreatment status and correction of possible electrolyte imbalance has been made, resume at next lower dose level.
QTc 481-500 ms	Hold. Seek cardiologist advice, patient may resume at next lower dose level if cardiologist agrees.
QTc \geq 501 ms	Discontinue treatment. Seek cardiologist advice.
Shift from baseline of \geq 60ms	Discontinue treatment. Seek cardiologist advice.

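### The 21-day toxicity rules in Sections 6.7, 6.7.2 and 6.7.3 disagree on Medical Monitor approval, on the clock, and on whether the patient leaves treatment or the study

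*Protocol*

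**What the plan says.** Three sentences in the protocol set a 21-day limit for stopping because of toxicity.

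- Section 6.7 covers any patient. One whose toxicity delays dosing by more than 21 days, counted from when the next dose was due, "must be discontinued from the study unless there is approval from the Medical Monitor for the patient to continue".
- Section 6.7.2, under Table 9: "If haematologic toxicity parameters do not recover within 21 days, the patient should be removed from the study treatment". No approval route is given.
- Section 6.7.3, for Grade 3 or 4 non-haematologic toxicity: a patient whose toxicity has not resolved to Grade 1 or lower "within 21 days should be removed from the study treatment unless approved by the Medical Monitor".

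Table 2 footnote o (BID schedule) uses the off-study wording as well: "Patients with progressive disease or unacceptable toxicity should be discontinued from the study".

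Elsewhere the protocol separates stopping drug from leaving the study. Section 3.9.1 explains what it means to "withdraw from the study (i.e., investigational product and assessments". Section 5.1.1 runs imaging "until objective disease progression as defined by RECIST v1.1 or withdrawal from study". Section 4.2 counts a patient in efficacy follow-up after treatment as still on study.

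**The concern.** Section 6.7 applies to every patient, so a patient with slow haematologic recovery falls under both it and the line below Table 9. The first lets that patient continue if the Medical Monitor agrees; the second does not. Sites could treat the same patient differently while each follows the protocol.

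The second issue is what stops. A site that takes a patient off the study under Section 6.7, and reads that as Sections 3.9.1 and 5.1.1 define it, ends scans and assessments. The patient has only stopped drug without progression, and other sections require follow-up in that case. At stake are consistent handling of prolonged toxicity and complete data on how that toxicity resolves. Safety and tolerability is a secondary objective.

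**Working it through.** The plan states no figure to reproduce. The check sets the passages side by side and does day arithmetic on the dosing schedules.

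**Step 1. The three rules.**

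| | Section 6.7 | Section 6.7.2 | Section 6.7.3 |
|---|---|---|---|
| Who | Any patient | Haematologic | Grade 3 or 4 non-haematologic |
| What is counted | Dose delay | Time to recovery | Time to resolution |
| Clock starts | Intended next dose | Not stated | Not stated |
| Medical Monitor approval | Yes | No | Yes |
| Patient leaves | Study | Study treatment | Study treatment |

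Sections 6.7.2 and 6.7.3 cover different toxicity classes, so a difference between those two could be intended. Each of them conflicts with Section 6.7.

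**Step 2. The approval conflict needs no clock assumption.** Table 9 applies on cycle Day 1 and delays in one-week steps, so its 21 days most naturally run from the day the dose was due (3 × 7 = 21). On 5/9 the next cycle is due on Day 15, and both limits fall on 15 + 21 = Day 36. On either 5/2 schedule it is due on Day 22, and both fall on 22 + 21 = Day 43. On the same day, one rule allows continuation with approval and the other gives no such route.

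**Step 3. The clock in Section 6.7.3.** Assume that its clock starts on day *t*, when the toxicity is found, that dosing is held at once, and that the next scheduled dose is on day *n*. The gap is (*n* + 21) − (*t* + 21) = *n* − *t*.

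| Schedule | Largest gap | Smallest gap |
|---|---|---|
| 5/9 | found Day 5, due Day 15: 10 days | found Day 15: 0 |
| 5/2 | found Day 12, due Day 22: 10 days | found Day 22: 0 |
| 5/2 weekly | found Day 19, due Day 22: 3 days | found Day 22: 0 |

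For example, toxicity found on Day 8 of 5/9 gives Day 29 against Day 36, a gap of 7 days. If the clock starts instead on the day the dose was due, the gap is 0 throughout.

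**Step 4. Study against study treatment.** These requirements continue after drug stops and cannot be met if the patient is off the study as Section 3.9.1 describes it:

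- Section 4.3.1: Grade 3 or 4 laboratory abnormalities present at discontinuation are followed until Grade 1 or 2.
- Section 4.3.2.1: scans continue to progression.
- Section 4.3.2.2: survival follow-up after progression. Footnote o conflicts with this because it also takes progressing patients off the study.
- Section 6.3.1: ongoing AEs are followed after stopping for a reason other than progression.
- Table 10, most severe rows: treatment stops and the patient is followed for progression.

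**Step 5. How much would be lost.**

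- *New AEs.* Collection ends 30 days after the last dose (Section 6.3.1). For a delayed next cycle, the Section 6.7 limit comes 36 − 5 = 31 days after the last dose on 5/9, 43 − 12 = 31 on 5/2 and 43 − 19 = 24 on 5/2 weekly. For a mid-cycle hold it comes 22 to 24 days after. At most 30 − 22 = 8 days of the window remain, and often none.
- *PFS.* Scans after stopping without progression are every 3 months (table footnotes), about 90 days. Section 8.4.6 censors progression or death seen more than 35 days (5/9) or 53 days (BID, 5/2) after the previous evaluable assessment. Most progressions first seen on these scans would be censored in any case.
- *DLT.* Section 7.2.2 can already count a toxicity that disrupts dosing for more than 7 days, well before a 21-day limit.

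**The case against.** The strongest reply is that *study* is loose shorthand for *treatment*. Footnote o removes progressing patients from the study although Section 4.3.2.2 follows them for survival, and its sentence contrasts them with patients who continue treatment. Section 6.7.1 speaks of suspending the study where Section 6.7.3 says investigational product. The off-treatment footnotes (s in Table 2, u in Tables 3 and 4) follow all patients until toxicity resolves, for at least 30 days, or until new therapy. This makes the benign reading plausible but does not settle it. Just before its 21-day rule, Section 6.7 says study drug for patients needing more than two reductions, and Section 3.10 lists an AE as a reason to withdraw from the study.

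It can also be said that a specific rule displaces a general one, so Section 6.7.2 governs haematologic cases. The protocol states no such order. Section 6.7.3 is equally specific and does repeat the approval route, so the silence in Section 6.7.2 could be deliberate or an omission.

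A third reply is that the effect is now small: all schedules are closed to enrolment, footnote o concerns only the completed BID cohorts, and Version 5 plans no further statistical analysis after the primary cut-off. That limits the consequence. However, Section 4.3.2.3 tells investigators of continuing patients to follow, in general, the protocol's approach to reduction and discontinuation, so the conflicting text remains in use.

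A reader might infer more than the documents support: that the rules differ by a fixed number of days, that the patients with the worst toxicity are lost, that late SAEs go unreported, or that PFS is materially biased. The gap can be 0. Table 10 keeps the most severe haematologic cases in progression follow-up. Section 6.3.2 keeps a route for related SAEs learned of after the study. The censoring rule in Section 8.4.6 already removes most of the PFS information concerned, and PFS is not a listed objective.

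**Conclusion.** The conflict is real and worth correcting, but it is one of wording with limited statistical consequence. Two parts rest on the text alone: the clash over Medical Monitor approval in slow haematologic recovery, and the contradiction between going off study and the required follow-up. The timing difference between Sections 6.7 and 6.7.3 is 0 to 10 days on 5/9 and 5/2, and 0 to 3 days on 5/2 weekly. It depends on a clock start that the protocol does not give, and on dosing being held at once.

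If sites read the off-study wording literally, the likely loss is follow-up of unresolved toxicity and off-treatment scans in patients with prolonged toxicity, who are not necessarily those with the worst. The effect on new-AE capture and on the DLT primary endpoint is small. The small effect on PFS holds for the 35- and 53-day windows as written; longer windows would make the lost scans matter more.

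**What to change.** Reconcile Sections 6.7, 6.7.2 and 6.7.3 so that they state consistently when the 21 days start and whether Medical Monitor approval applies. If the rule is meant to differ by toxicity class, Section 6.7 should say so. Which clock and which approval rule to keep is the sponsor's choice.

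Separately, reconcile the off-study wording in Section 6.7 and Table 2 footnote o with Sections 4.3 and 6.3.1 and Table 10, so that stopping for toxicity does not end follow-up that the protocol requires elsewhere.

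The cost is protocol wording only, with no change to sample size, visits or analysis.
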